2.0 STUDY SUMMARY

Study Title	Prospective, Multi-center, Single-arm Feasibility Study of the Shockwave Medical Mini S Peripheral Intravascular Lithotripsy (IVL) System (Mini S Feasibility Study)
Study Objective	To assess the safety and performance of the Shockwave Medical Mini S Peripheral IVL System for the treatment of heavily calcified, stenotic peripheral arteries.
Study Device(s)	Shockwave Medical Peripheral IVL System with Mini S IVL Catheter (Standard and Flex configurations)
Indications for Use	The Mini S IVL Catheter is intended for lithotripsy-enhanced catheter dilatation of lesions, including calcified lesions found in the peripheral vasculature, such as the iliac, femoral, ilio-femoral, popliteal, infra-popliteal, and renal arteries. The Mini S IVL Catheter is not for use in the coronary or cerebral vasculature.
Study Design	Prospective, multi-center, single-arm feasibility study
Enrollment	Up to 50 subjects with a minimum of 10 BTK lesions treated at up to 6 sites in Australia and New Zealand. A maximum of two (2) target lesions may be treated per subject.
Study Duration / Follow-Up Period	Subjects will be followed through discharge, 30 days, 6 and 12 months. Duplex Ultrasound (DUS) assessments required at 12 months. Total anticipated study duration approximately 26 months.
Subject Population	Subjects with moderate to severely calcified peripheral artery disease (PAD) with target lesion located in a native, de novo superficial femoral, popliteal or infrapopliteal artery.
Primary Safety Endpoint	Major Adverse Events (MAE) at 30 days defined as a composite of: 
 ○ Cardiovascular death ○ Clinically-driven target lesion revascularization (CD-TLR) ○ Unplanned target limb major amputation (above the ankle)
Primary Performance Endpoint	Technical Success defined as final residual stenosis ≤50% without flow-limiting dissection (≥ Grade D) of the target lesion by angiographic core lab.

	No.: CP 65324	REV. D
	TITLE: Mini S Feasibility Study Protocol	
	CLASS: CLINICAL PROTOCOL	

	
4. Estimated life expectancy > 1 year.
 
5. Rutherford Clinical Category 2, 3, 4 or 5 of the target limb(s).
 
Angiographic Inclusion Criteria
 
6. One or two target lesion(s) located in a native de novo superficial femoral, popliteal or infrapopliteal artery (above the ankle joint), in one or both limbs.
 
7. Target lesion reference vessel diameter (RVD) between 2.0 mm and 7.0 mm by investigator visual estimate.
 
8. Target lesion stenosis $\geq 70\%$ (for vessels below the knee defined as P3 to the ankle joint) or $\geq 90\%$ (for vessels above the knee) by investigator visual estimate.
 
9. Target lesion length is ≤ 150 mm by investigator visual estimate. Target lesion can be all or part of the 150 mm treated zone.
 
 • Tandem lesions (lesions < 3 cm apart) are allowed if the total treated area covers the entire diseased segment. Total treated area is defined as the area treated by any device (pre-dilatation, IVL, post-dilatation, or destination therapy). Each tandem lesion/diseased segment is considered one target lesion. • If these segments are treated independently (i.e., no PTA treatment between two lesions) then this is considered two separate target lesions. 
10. Calcification is at least moderate defined as presence of fluoroscopic evidence of calcification: 1) on parallel sides of the vessel and 2) extending $> 50\%$ the length of the lesion if lesion is ≥ 50 mm in length; or extending for minimum of 20mm if lesion is < 50 mm in length.

Study Exclusion Criteria	
General Exclusion Criteria
 
1. Rutherford Clinical Category 0, 1 and 6 (target limb).
 
2. History of endovascular or surgical procedure on the target limb within the last 30 days, or planned within 30 days of the index procedure, with the exception of toe amputation. Note: inflow treatment of non-target lesions is allowed providing successful treatment.
 
3. Subject in whom antiplatelet or anticoagulant therapy is contraindicated.

	No.: CP 65324	REV. D
	TITLE: Mini S Feasibility Study Protocol	
	CLASS: CLINICAL PROTOCOL	PAGE 10 OF 70

	
4. Subject has known allergy to contrast agents or medications used to perform endovascular intervention that cannot be adequately pre-treated.
 
5. Subject has known allergy to urethane, nylon, or silicone.
 
6. Myocardial infarction within 60 days prior to enrollment.
 
7. History of stroke within 60 days prior to enrollment.
 
8. Subject has acute or chronic renal disease with eGFR <30 ml/min/1.73 m² (using CKD-EPI formula), unless on renal replacement therapy.
 
9. Subject is pregnant or nursing.
 
10. Subject is participating in another research study involving an investigational agent (pharmaceutical, biologic, or medical device) that has not reached the primary endpoint.
 
11. Subject has other medical, social or psychological problems that, in the opinion of the investigator, preclude them from receiving this treatment, and the procedures and evaluations pre- and post-treatment.
 
12. Covid-19 diagnosis within 30 days.
 
13. Planned use of cutting/scoring balloons, re-entry or atherectomy devices in target lesion(s) during the index procedure.
 
14. Planned major amputation of target limb.
 
15. Acute limb ischemia.
 
16. Occlusion of all the inframalleolar outflow arteries/vessels (i.e., desert foot).
 
17. Subject already enrolled into this study.
 
Angiographic Exclusion Criteria
 
18. Failure to successfully treat clinically significant inflow lesions in the ipsilateral iliac, femoral, or popliteal arteries, defined as ≤30% residual stenosis with no serious angiographic complications (e.g. embolism).
 
19. Failure to successfully treat significant non-target infra-popliteal lesions, if treated prior to treatment of target lesion(s). Successful treatment is defined as obtaining ≤50% residual stenosis with no serious angiographic complications (e.g., embolism).
 
20. Target lesion includes in-stent restenosis.

--	--

	No.: CP 65324	REV. D
	TITLE: Mini S Feasibility Study Protocol	
	CLASS: CLINICAL PROTOCOL	PAGE 11 OF 70

	
21. Evidence of aneurysm or thrombus in target vessel.
 
22. No calcium or mild calcium in the target lesion.
 
23. Target lesion within native or synthetic vessel grafts.
 
24. Failure to successfully cross the guidewire across the target lesion; successful crossing defined as tip of the guidewire distal to the target lesion in the absence of flow limiting dissections or perforations.

Study Statistical Methods	Descriptive statistics will be reported.

	No.: CP 65324	REV. D
	TITLE: Mini S Feasibility Study Protocol	
	CLASS: CLINICAL PROTOCOL	PAGE 12 OF 70

The figure consists of a 10x10 grid of horizontal bars. The bars are black and vary in length. The grid is divided into two main sections by a vertical line: the left section has 5 rows and the right section has 5 rows. The bars are grouped by row, with the first bar of each row being the longest in the right section and the shortest in the left section. The bars in the right section generally increase in length from top to bottom, while in the left section they fluctuate.

	No.: CP 65324	REV. D
TITLE: Mini S Feasibility Study Protocol		
	CLASS: CLINICAL PROTOCOL	PAGE 13 OF 70

A horizontal bar chart with three groups of bars. The first group has 2 bars, the second has 7 bars, and the third has 5 bars. All bars are black and have a thin white outline. The bars in each group are of different lengths, representing the count of countries for each category.

Group	Category	Count
Group 1	Category A	2
	Category B	1
Group 2	Category C	3
	Category D	2
	Category E	4
	Category F	5
	Category G	3
	Category H	2
	Category I	1
Group 3	Category J	2
	Category K	3
	Category L	4
	Category M	2
	Category N	1

	No.: CP 65324	REV. D
	TITLE: Mini S Feasibility Study Protocol	
	CLASS: CLINICAL PROTOCOL	PAGE 14 OF 70

3.0 INTRODUCTION

3.1 Background

3.1.1 Peripheral Arterial Disease

Peripheral arterial disease (PAD) is one of the most common indications of atherosclerotic disease and impacts more than 200 million people globally [1]. PAD is caused by the accumulation of plaque in the arteries that do not supply the brain or the heart. Although it can involve the renal arteries and/or the arteries of the neck or arms, PAD normally develops in the lower extremities. The reduced blood flow may lead to pain, tissue loss and eventual foot/leg amputation or death. Risk factors for PAD include advanced age, smoking, hypertension, diabetes and concomitant cardiovascular disease [1]. Calcified PAD is associated with coronary artery disease, diabetes and chronic kidney disease [2].

Early diagnosis and treatment of PAD reduces an individual's risk of cardio- or cerebrovascular disease morbidity and mortality [3]. Percutaneous endovascular therapies are being increasingly employed as the primary revascularization treatment for PAD, including calcified occlusions [4-6]. Endovascular therapies include percutaneous angioplasty (PTA), nitinol stents, directional and rotational atherectomy, laser atherectomy, drug-eluting stents (DES) and drug-coated balloons (DCB) [6].

Infrapopliteal atherosclerosis is a multilevel disease affecting below-the-knee (BTK) arteries and is often associated with critical limb ischemia (CLI). CLI represents the most severe form of PAD and is characterized by ischemic rest pain and/or nonhealing ulcers [7]. BTK lesions are often technically challenging to treat due to long length, small vessel diameter, poor outflow, and severe calcification [8]. Vessel wall calcification is more severe in BTK lesions compared to more proximal lesions, with medial calcification being most prevalent in the infrapopliteal segment. Due to the severity and unequal distribution of calcium in infrapopliteal lesions, vessel wall expansion can occur in a non-uniform manner increasing the risk for severe dissection with high pressure balloon dilatation [8]. Procedural success for infrapopliteal lesions has improved; however, recoil, dissections, and restenosis remain limitations of infrapopliteal endovascular procedures [9].

In sub-total occlusions with the narrowest crossing channels, microcatheters, with soft tips, tapered shapes, and variety of wire selections may be used to cross a lesion and allow for subsequent dilatation. Nevertheless, severe tortuosity and severe calcification remain barriers to microcatheter success, leading to excessively high rates of complications (typically either dissection and/or perforation) [10].

3.1.2 Intravascular Lithotripsy

Intravascular lithotripsy is a balloon-based calcium modification treatment modality that uses acoustic pressure waves to modify vessel wall calcium. Peripheral IVL is designed to improve vessel wall compliance to optimize acute gain while minimizing acute vessel injury. The safety and effectiveness of IVL has been reported in several clinical studies in moderate to severely

	No.: CP 65324	REV. D
	TITLE: Mini S Feasibility Study Protocol	
	CLASS: CLINICAL PROTOCOL	PAGE 15 OF 70

calcified PAD across multiple vessel beds [11-19], including the Disrupt PAD BTK study and the Disrupt PAD III Observational Study (OS), which evaluated peripheral IVL in BTK lesions.

The DISRUPT BTK study enrolled 20 patients with moderate to severely calcified infrapopliteal lesions with 30-day follow-up [14]. After treatment with IVL using the first generation M⁵ catheter, all patients achieved a residual stenosis <50%. There was only one type B dissection, and a total of two (2) stents were placed. These initial promising results supported the use of IVL to maximize lumen gain while minimizing dissections when treating severely calcified infrapopliteal lesions.

Introduction of the Shockwave S⁴ IVL catheter allowed for expanded treatment of BTK lesions due to a smaller crossing profile and balloon diameters relative to the M⁵ catheter. Adams et al recently analyzed a cohort of patients from the PAD III Observational Study (OS) with calcified BTK disease treated with the S⁴ IVL catheter [11]. A total of 101 patients with 114 calcified infrapopliteal arteries were enrolled at 15 sites and were followed through discharge. This study included a challenging patient and lesion cohort with 69% of patients presenting with CLI and 35% with CTO lesions. The continued safety and effectiveness of peripheral IVL was demonstrated as 99% of lesions achieved a residual stenosis < 50% with no occurrences of serious angiographic complications at the end of the procedure, regardless of BTK lesion location.

3.1.3 Mini S IVL Catheter

The Mini S catheter is designed to leverage the same safety and effectiveness of IVL balloon catheters (M⁵ and S⁴) but represents a low-profile option with a distally-shifted emitter that can be used in sub-total occlusions with extremely narrow crossing channels where other devices may be challenged today.

The Shockwave Mini S Peripheral IVL Catheter has equivalent base materials and similar technological characteristics as the predicate device Shockwave S⁴ Peripheral IVL Catheter. The Mini S and S⁴ IVL Catheters have similar emitter designs that deliver unfocused intermittent acoustic pulses at the same pulse rate and treatment frequency at low treatment pressures. Sonic output mapping of the Mini S and S⁴ IVL Catheters demonstrate that the average sonic output emitted by both devices have similar peaks and distribution and are within the same magnitude and standard deviation. These parameters have shown to be effective in treating calcified lesions with the S4 IVL Catheter and are applicable to the Mini S given the demonstrated equivalence.

Human cadaveric studies were conducted to assess the Mini S trackability, ability to cross and modify calcium, the visibility of the emitter band under fluoroscopy, and interaction with ancillary devices. The device was found to have an acceptable level of pushability/trackability, deliverability/crossability, emitter visibility, catheter working length and overall durability. These cadaver labs provided confirmation that Mini S IVL catheter functioned as intended by modifying calcium to allow for further treatment at the physician's discretion. Additional information regarding the pre-clinical studies can be found in the Investigator Brochure (IB 65349).

	No.: CP 65324	REV. D
	TITLE: Mini S Feasibility Study Protocol	
	CLASS: CLINICAL PROTOCOL	PAGE 16 OF 70

3.2 Study Rationale

The Mini S Feasibility study is being conducted to assess the safety and performance of the Shockwave Medical Mini S Peripheral IVL System for the treatment of heavily calcified, stenotic peripheral arteries.

	No.: CP 65324	REV. D
	TITLE: Mini S Feasibility Study Protocol	
	CLASS: CLINICAL PROTOCOL	PAGE 17 OF 70

4.0 STUDY DEVICE / TEST ARTICLE DESCRIPTION

4.1 Mini S Peripheral IVL Catheter

The Shockwave Mini S Peripheral IVL Catheter is a proprietary lithotripsy device delivered through the peripheral arterial system of the lower extremities to the site of an otherwise difficult to treat calcified stenosis. Energizing the lithotripsy device will generate pulsatile mechanical energy within the target treatment site, disrupting calcium within the lesion and allowing subsequent dilatation of a peripheral artery stenosis. The Mini S IVL Catheter comprises a distal lithotripsy emitter for the localized delivery of pulsatile mechanical energy.

The Mini S IVL Catheter shaft contains a lumen to pressurize and flush the catheter, a guidewire lumen, and a lithotripsy emitter. The lumen is used to pressurize and flush the catheter with saline. The guidewire lumen enables the use of a 0.014" (0.36mm) guidewire to facilitate advancement of the catheter to and through the target stenosis. The system is designed as 'Over-the-wire' (OTW) with 150cm shaft working length. The emitter is positioned at the distal end of the catheter for delivery of pulsatile mechanical energy. The Mini S Catheter has a hydrophilic coating on the distal end designed to increase lubricity during advancement of the catheter to the treatment site. The emitter is radiopaque to facilitate catheter visibility under fluoroscopy and it is surrounded by an IVL Window that allows for the transmission of pulsatile mechanical energy. The proximal hub has three ports: one to pressurize and flush the system, one for guidewire lumen, and one for connection to the IVL Connector Cable. Refer to **Figure 1** below for IVL Catheter components.

The Mini S Peripheral IVL Catheter is available in two configurations: Standard and Flex. For easy identification, Standard has a blue shaft extrusion color and Flex has a yellow shaft. The Mini S Standard has a 15 cm distal segment, and the Flex has a 25 cm distal segment for more flexibility. The IVL Catheter is compatible with a 5Fr sheath and has a working length of 150cm. Both configurations will be evaluated in the Mini S Feasibility study.

The Mini S IVL Catheter is part of the Peripheral IVL System. The system consists of the IVL Catheter, an IVL Connector Cable and an IVL Generator. The Mini S IVL Catheter is to be used exclusively with the IVL Generator and its accessories. The IVL Generator and Connector Cable are not investigational; they are supplied non-sterile and are reusable. Refer to the *Shockwave Medical, Inc. IVL Generator and Connector Cable Operator's Manual* for preparation, operation, warnings and precautions, and maintenance of the IVL Generator and IVL Connector Cable. The IVL Catheter is supplied sterile via E-beam sterilization. It is intended for single use only and is not intended for reuse or re-sterilization. Refer to the Instructions for Use (IFU) for a complete product description.

4.1.1 Mini S IVL Catheter Design Modification

The Mini S IVL Catheter has incorporated a design modification as part of continuous improvement. Two modifications were made to the Mini S IVL Catheter, the distance between the emitter and the distal tip and the shaft extrusion color. The emitter to distal tip length has been shortened on both configurations, Standard and Flex. A shorter distance between the emitter and the distal tip optimized energy delivery to facilitate crossing. There is no change to the energy profile or sonic output specification. The shaft extrusion color for Flex has been

	No.: CP 65324	REV. D
	TITLE: Mini S Feasibility Study Protocol	
	CLASS: CLINICAL PROTOCOL	PAGE 18 OF 70

changed from blue to yellow to allow for easier identification of both configurations during the manufacturing process and during use. The Standard configuration remains blue. The modifications do not alter the intended use or principles of operation, and the changes do not introduce new hazards which had not been previously addressed. More information regarding these design modifications to the Mini S IVL Catheter can be found in the Investigator Brochure (IB 65349).

[figure not shown]

Figure 1. Shockwave Mini S Peripheral IVL Catheter

4.2 Indication for Use

The Mini S IVL Catheter is intended for lithotripsy-enhanced catheter dilatation of lesions, including calcified lesions found in the peripheral vasculature, such as the iliac, femoral, ilio-femoral, popliteal, infra-popliteal, and renal arteries. The Mini S IVL Catheter is not for use in the coronary or cerebral vasculature.

	No.: CP 65324	REV. D
	TITLE: Mini S Feasibility Study Protocol	
	CLASS: CLINICAL PROTOCOL	PAGE 19 OF 70

5.0 STUDY OBJECTIVES

The objective of this study is to assess the safety and performance of the Shockwave Medical Mini S Peripheral IVL System for the treatment of heavily calcified, stenotic peripheral arteries.

5.1 Safety Endpoints

The safety endpoints for this study include:

- **PRIMARY: Major Adverse Events (MAE)** at 30 days defined as a composite of:
 - Cardiovascular death
 - Clinically-driven target lesion revascularization (CD-TLR)
 - Unplanned target limb major amputation (above the ankle)
- **Serious angiographic complications** defined as flow-limiting dissection (\geq grade D), perforation, distal embolization, or acute vessel closure as assessed by the angiographic core lab.
- **MAE** at 6 and 12 months (as a composite and individual components)

5.2 Performance Endpoints

The performance endpoints are listed below. Device endpoints will be reported for all Mini S IVL Catheters.

- **PRIMARY: Technical Success** defined as *final* residual stenosis \leq 50% without flow-limiting dissection (\geq Grade D) of the target lesion by angiographic core lab.
- **IVL Technical Success (post-dil)** defined as *post-dilatation* residual stenosis \leq 50% without flow-limiting dissection (\geq Grade D) of the target lesion by angiographic core lab (measured immediately following mandatory post-dilatation).
- **IVL Device Success** defined as the ability to deliver, advance across the target lesion, pressurize, pulse, flush and retrieve the Mini S IVL Catheter.
- **Technical Success (final)** defined as *final* residual stenosis \leq 30% without flow-limiting dissection (\geq Grade D) of the target lesion by angiographic core lab.
- **Primary Patency** at 12 months defined as:
 - Above the knee lesions: freedom from \geq 50% restenosis as determined by Duplex Ultrasound (DUS) and freedom from Clinically-Driven Target Lesion Revascularization (CD-TLR)
 - Below the knee lesions: freedom from both total occlusion (100% diameter stenosis by DUS) in all of the target lesions in a flow pathway, as well as a CD-TLR

	No.: CP 65324	REV. D
	TITLE: Mini S Feasibility Study Protocol	
	CLASS: CLINICAL PROTOCOL	PAGE 20 OF 70

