7.2 Subject Selection

7.2.1 Inclusion Criteria

Subjects are required to meet all of the following inclusion criteria in order to be enrolled in the study. For lesion characteristics, each target lesion must meet eligibility. A maximum of two (2) target lesions may be treated per subject; target lesions may be in the same limb or in different limbs.

General Inclusion Criteria

1. Age of subject is \geq 18 years.
2. Subject is able and willing to comply with all assessments in the study.
3. Subject or subject's legal representative has been informed of the nature of the study, agrees to participate, and has signed the approved consent form.
4. Estimated life expectancy $>$ 1 year.
5. Rutherford Clinical Category 2, 3, 4 or 5 of the target limb(s).

Angiographic Inclusion Criteria

6. One or two target lesion(s) located in a native de novo superficial femoral, popliteal or infrapopliteal artery (above the ankle joint), in one or both limbs.

	No.: CP 65324	REV. D
	TITLE: Mini S Feasibility Study Protocol	
	CLASS: CLINICAL PROTOCOL	PAGE 22 OF 70

7. Target lesion reference vessel diameter (RVD) between 2.0 mm and 7.0 mm by investigator visual estimate.
8. Target lesion stenosis $\geq 70\%$ (for vessels below the knee, defined as P3 to the ankle joint) or $\geq 90\%$ (for vessels above the knee) by investigator visual estimate.
9. Target lesion length is ≤ 150 mm by investigator visual estimate. Target lesion can be all or part of the 150 mm treated zone.
 - Tandem lesions (lesions < 3 cm apart) are allowed if the total treated area covers the entire diseased segment. Total treated area is defined as the area treated by any device (pre-dilatation, IVL, post-dilatation, or destination therapy). Each tandem lesion/diseased segment is considered one target lesion.
 - If these segments are treated independently (i.e., no PTA treatment between two lesions) then this is considered two separate target lesions.
10. Calcification is at least moderate defined as presence of fluoroscopic evidence of calcification: 1) on parallel sides of the vessel and 2) extending $> 50\%$ the length of the lesion if lesion is ≥ 50 mm in length; or extending for minimum of 20mm if lesion is < 50 mm in length.

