9.2.2 Primary Performance Endpoint

Technical Success defined as final residual stenosis $\leq 50\%$ without flow-limiting dissection (\geq Grade D) of the lesion by angiographic core lab. Primary Performance will be assessed on a per-lesion basis.

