	CLASS: CLINICAL PROTOCOL	

Limb Ischemia: Deficient supply of oxygenated blood to the tissues in the limbs that is due to obstruction of the inflow of arterial blood characterized by pain and/or discoloration of the limb.

Lithotripsy: A medical procedure for disrupting calculus in the body.

Luminal Patency: Post-procedure residual stenosis <50% as determined by investigator visual assessment or quantitative analysis of the end of procedure angiogram.

Major Adverse Event (MAE): For the purposes of this study, the definition of Major Adverse Event(s) includes:

- cardiovascular death
- target lesion revascularization
- Unplanned target limb major amputation (above the ankle)

Perforation: Puncture of an arterial wall.

Restenosis: Reoccurrence of narrowing or blockage of target lesion.

Rutherford Classification of Critical Limb Ischemia: Clinical staging system for describing PAD. It includes 7 categories:

Grade	Category	Clinical Description
0	0	Asymptomatic
I	1	Mild claudication
	2	Moderate claudication
I	3	Severe claudication
	4	Ischemic rest pain
II	5	Ischemia ulceration not exceeding ulcer of the digits of the foot
III	6	Severe ischemic ulcers or frank gangrene
IV		

ACC/AHA/SCIA/SIR/SVM 2018 Appropriate Use Criteria for Peripheral Artery Intervention – Bailey et al. 2019)

Serious Adverse Device Effect (SADE): Adverse device effect that has resulted in any of the consequences characteristic of a serious adverse even.

Serious Adverse Event (SAE): Adverse event that led to any of the following:

- death,

	No.: CP 65324	REV. D
	TITLE: Mini S Feasibility Study Protocol	
	CLASS: CLINICAL PROTOCOL	

- serious deterioration in the health of the subject, user, or other persons as defined by one or more of the following:
 - a life-threatening illness or injury, or
 - a permanent impairment of a body structure or a body function including chronic diseases, or
 - in-patient or prolonged hospitalization, or
 - medical or surgical intervention to prevent life-threatening illness or injury, or permanent impairment to body structure or a body function,
 - foetal distress, foetal death, a congenital abnormality, or birth defect including physical or mental impairment.

Note: Planned hospitalization for a pre-existing condition, or a procedure required by the CIP, without serious deterioration in health, is not considered a serious adverse event.

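### A below-the-knee lesion that fails Technical Success at index can be scored primary patent at 12 months if it neither occludes nor has a CD-TLR

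*Protocol*

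**What the plan says.** Section 5.2, repeated in the Study Summary (2.0), sets separate patency rules by level.

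- **Above the knee:** patency is lost at 50% or more "restenosis as determined by Duplex Ultrasound (DUS) and freedom from Clinically-Driven Target Lesion Revascularization (CD-TLR").
- **Below the knee:** the imaging test is "Below the knee lesions: freedom from both total occlusion (100% diameter stenosis by DUS"). The bullet then continues "in all of the target lesions in a flow pathway, as well as a CD-TLR", so CD-TLR is a second failure route.

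Other provisions that bear on the rule:

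- **Entry (7.2.1, criterion 8):** stenosis of at least 70% "for vessels below the knee, defined as P3 to the ankle joint", with no upper limit. Section 3.1.3 says the catheter "can be used in sub-total occlusions with extremely narrow crossing channels".
- **Technical Success (5.2, 9.2.2):** final core-lab residual stenosis of at most 50% with no dissection of Grade D or worse. "Primary Performance will be assessed on a per-lesion basis".
- **Analysis set (9.4, 7.7.4):** all enrolled subjects, with enrollment complete once the catheter enters the body over a guidewire that has crossed the lesion. Under 7.7.6, a catheter that cannot cross the lesion is an IVL Device Failure and the subject goes on to standard care.
- **CD-TLR (15.1):** requires an actual repeat revascularization of a lesion at 50% or more, with ischemia or recurrence of the presenting syndrome.

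**The concern.** Any BTK lesion entering at 70-99% already passes the no-occlusion test before treatment. Nothing in the definition asks whether the lesion was ever opened, and failed procedures stay in the analysis set. CD-TLR catches a failed procedure only if it leads to a clinically driven re-treatment. A persistent severe stenosis that is left alone is not an event.

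The misclassification runs in one direction, towards success. Duplex ultrasound is scheduled only at 12 months, so this endpoint is the study's one scheduled imaging measure of durability. Section 6.2 says the study should inform later development and the parameters of a pivotal investigation, and 12.9 foresees use in publications and regulatory submissions. A BTK patency rate that includes lesions never opened would be a poor planning figure, and with so few BTK lesions guaranteed, one such lesion shows.

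**Working it through.** The protocol gives no patency figure to reproduce and has no hypothesis or power calculation (9.3). The check therefore applies the stated rules to given stenosis values and then sizes the effect.

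**Step 1. Apply the rules.** The stenosis is taken as left at index and unchanged at 12 months, with no flow-limiting dissection and no CD-TLR.

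| Stenosis | Meets BTK entry (≥70%) | Technical Success (≤50%) | BTK patent (<100%) | Above-knee patent (<50%) |
|---|---|---|---|---|
| 30% | no | yes | yes | yes |
| 51% | no | no | yes | no |
| 70% | yes | no | yes | no |
| 90% | yes | no | yes | no |
| 99% | yes | no | yes | no |
| 100% | yes | no | no | no |

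From 51% to 99%, a BTK lesion fails Technical Success and is scored patent. The same stenosis above the knee is not patent. A lesion that is totally occluded at entry and is never opened fails the BTK test, so the gap concerns lesions that are sub-total at entry.

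**Step 2. Effect of one lesion.** The minimum number of BTK lesions is 10 (6.5). Taking the lesion as the unit, with all 10 evaluable, one misclassified lesion adds 1/10 = 10 percentage points. For example, 9/10 becomes 10/10, and the exact interval (9.1; 95% level assumed, since none is stated) moves from 55.5%-99.7% to 69.2%-100%.

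**Step 3. How many lesions.** The protocol gives no index failure rate for this device. Section 3.1.2 cites a BTK cohort treated with an earlier catheter in which 99% of lesions reached under 50% residual stenosis, a failure rate of about 1%. Rates of 5% and 10% are added as assumptions, because this is a first-in-human device aimed at very narrow channels. With failure rate f and 10 independent lesions:

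| f | Expected index failures, 10 × f | Chance of at least one, 1 − (1 − f)^10 |
|---|---|---|
| 1% (cited cohort) | 0.1 | 1 − 0.99^10 = 9.6% |
| 5% (assumed) | 0.5 | 1 − 0.95^10 = 40.1% |
| 10% (assumed) | 1.0 | 1 − 0.90^10 = 65.1% |

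Divided by 10 lesions, the expected inflation is at most 1, 5 or 10 percentage points. These are upper bounds, because a failed lesion is misclassified only if it is also open and free of CD-TLR at 12 months.

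**The case against.** The strongest reply is that index failure is already reported, and more prominently. Technical Success is the primary performance endpoint and is assessed per lesion. Post-dilatation success, a 30% final threshold and IVL Device Success are reported as well. A lesion left at 80% fails the primary endpoint whatever its 12-month status. ABI or TBI and Rutherford category are collected at 12 months, and the MAE components, CD-TLR among them, are reported individually. Patency is a secondary, descriptive endpoint in a study without hypotheses. Sections 7.7.9 and 7.7.10 also provide for further treatment of residual stenosis during the index procedure, which should keep failures few. Finally, an occlusion threshold below the knee is a defensible choice where ultrasound grading is less precise.

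Most of this stands, and it limits the weight of the point. It does not change how the rule scores an unopened lesion. Separate reporting of the acute failure does not stop the 12-month rate from counting that lesion as a success.

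Three stronger readings are tempting and are not supported:

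- **That BTK patency fails only at 100% occlusion.** CD-TLR is a stated second route.
- **That about 65% of BTK lesions would be misclassified,** from the 35% with total occlusions in the cited cohort (100% − 35%). The 35% is stated for patients, not lesions. The remainder is the share passing one component at baseline, not the share wrongly scored. For a lesion that was opened, later occlusion is a real loss that the endpoint detects.
- **That the above-knee rule has the same gap,** because 15.1 defines restenosis as "Reoccurrence of narrowing or blockage of target lesion" and an unopened lesion cannot recur. With one scheduled ultrasound and a 50% threshold, the rule will in practice be read as stenosis of 50% or more, and such a lesion fails.

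**Conclusion.** The point holds as a gap in the definition. A BTK lesion that is sub-total at entry, fails Technical Success at index, and is neither occluded nor re-treated for clinical reasons by 12 months is scored primary patent by the stated rule.

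The number of such lesions is probably small: about 0.1 expected in 10 BTK lesions at the cited cohort's failure rate, and 0.5 to 1 at assumed rates of 5-10%. Each one is worth 10 percentage points at the minimum of 10 lesions, and less with more. This rests on the lesion being the unit of analysis. The wording about all target lesions in a flow pathway could be read as requiring every one of them to be occluded, which would be more lenient still.

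A reader might go further and infer that the endpoint cannot tell a durable result from no effect. The documents do not support that, since occlusion and CD-TLR both remain detectable failures. The change is worth making because it is cheap and removes an error that can only favour the device. It affects no primary endpoint.

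**What to change.** In 2.0 and 5.2, add to the BTK patency definition: *A target lesion that fails Technical Success at the index procedure (final core-lab residual stenosis above 50%, or flow-limiting dissection of Grade D or worse) is counted as not patent at 12 months.* Naming both halves of Technical Success keeps the two endpoints consistent.

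Keep the present occlusion-based measure, labelled *freedom from occlusion and CD-TLR*. Beside it, report BTK lesions from the same 12-month ultrasound as below 50%, 50-99% or 100%.

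The cost is wording in two sections and one table. The core-lab final reading and the 12-month ultrasound are already required, and no treatment or visit changes. The stated BTK patency rate may be slightly lower, and ultrasound grading of non-occlusive stenosis in calcified BTK vessels is less precise, so the graded table should carry that caveat.
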